5.5.12. Reldesemtiv Concentration Bin

The average C_{trough} value from Weeks 2, 4, 8 and 12 as well as the average C_{max} value from Weeks 2 and 12 will be calculated for each patient who received reldesemtiv, and the averaged C_{trough} or C_{max} values will then be used to assign patients to one of the reldesemtiv concentration bins that are classified by selected ranges of percentiles. For example, a set of the concentration bins can be defined using the quartiles of averaged C_{trough} values as follows:

- Bin A: averaged C_{trough} ≤ Q1
- Bin B: Q1 < averaged C_{trough} ≤ Q2
- Bin C: Q2 < averaged C_{trough} ≤ Q3
- Bin D: averaged C_{trough} > Q3

where Q1, Q2 and Q3 represent the 1st, 2nd and 3rd quartiles of the averaged C_{trough} values, respectively. Approximately equal number of patients will be assigned to each reldesemtiv concentration bin.

5.6. Handling of Missing Data

5.6.1. Missing Efficacy Endpoints

The efficacy analysis will be performed using mixed effect model as specified. The model will provide unbiased results without imputation assuming that the missing patterns are missing at random (MAR). If the percentage of missing values in the primary efficacy endpoint is > 20%, sensitivity analyses assuming different missing data pattern will be conducted. Multiple imputation within the dose group of each missing data pattern will be performed using Markov chain Monte Carlo method.

5.6.2. Missing Start and Stop Dates for Prior and Concomitant Medication

Imputation of missing/partial dates will not be performed. The available year or year and month in a partial date will be used and will be compared to first dosing year, month and day to determine whether to include the medication in the medication history or as a concomitant medication. If the available data do not give sufficient information to classify the medication, the medication will be classified as concomitant medication.

5.6.3. Missing Dates of ALS Symptom Onset and Diagnosis

Imputation of missing/partial dates will not be performed. The available year or year and month in a partial date will be used to calculate the time from ALS symptom onset and the time from ALS diagnosis (in months). The following derivation rules will be used in sequence in the calculation:

- If the duration in days can be derived based on the available date information, the duration in months will be calculated as

$$\text{Duration in month} = \text{Duration in day} / 30.4375$$

- If the duration in months can be derived but not the duration in days, the derived duration in months will be used for data summary.
- If the duration in years can be derived but not the duration in days and months, the duration in months will be calculated as

$$\text{Duration in month} = \text{Duration in year} \times 12$$

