5.5.7. Calculated Rate of Pre-Study Disease Progression

Change in ALSFRS-R total score will be used to represent the status of ALS disease progression. The pre-study rate of disease progression evaluated at baseline will be calculated as the change in ALSFRS-R total score between the date of ALS symptom onset and the date at baseline. Assuming a patient has a ALSFRS-R total score of 48 at the time of ALS symptom onset, the rate of disease progression per month evaluated at baseline can be calculated as follows: $(48 - \text{ALSFRS-R total score at baseline}) / \text{months (30.25 days) since ALS symptom onset}$.

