7.3. Subgroup Analyses

To examine the consistency of the observed treatment effect and to gain insight into the effectiveness of reldesemtiv in subpopulations, subgroup analyses will be performed. Analyses of the primary endpoint (percent predicted SVC change from baseline to Week 12) and the secondary endpoints (slope of muscle strength mega score through Week 12, and ALSFRS-R score change from baseline to Week 12) will be conducted for the following subgroups if the sample size in each category of a subgroup is sufficient for statistical modeling convergence and sound interpretation of analysis results:

- Sex (male, female)
- Age group (< 65, ≥ 65 years old)
- Race (white, non-white)
- BMI at baseline (< 25 kg/m², ≥ 25 kg/m²)
- Riluzole and edaravone use status at baseline (use both, use riluzole only, use edaravone only, use neither)
- Percent predicted SVC at baseline (< 80%, ≥ 80%)
- ALSFRS-R total score at baseline (< 38, ≥ 38)
- ALSAQ-5 total score at baseline (< 150, ≥ 150)
- Geographic region (North America, Europe, Australia)
- Anatomic site of disease onset (limb, bulbar, cognitive, respiratory)
- Time since ALS symptom onset (< 2 years, ≥ 2 years)
- Time since ALS diagnosis (< 1 year, ≥ 1 year)
- Time since ALS diagnosis (< 6 months, ≥ 6 months)
- Pre-study rate of disease progression (1st tertile, 2nd tertile, and 3rd tertile)

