7.9. Exploratory Analyses

7.9.1. Joint Rank Test

Joint rank analyses using the combined assessment of function and survival (CAFS) ([Berry 2013](#)) will be conducted to account for survival time in the analyses of change in the percent predicted SVC and ALSFRS-R total score at Week 12, individually.

Each patient will be compared with all others in the analysis population in a pairwise manner on their survival status and the functional measurements, ie, changes from baseline in the percent predicted SVC or ALSFRS-R total score. A score of +1 or -1 will be assigned if one has better or worse outcome than the other, respectively. The following rule will be used:

- Patients who died are ranked worse than those who survived.
- Among patients who died, patients who died first are ranked worse.
- For patients who discontinued treatment early but were alive, comparison is based on the last time-point measurements that are both available for the patients in pairs. A patient is ranked worse if the patient discontinued treatment early and did not have functional measurement collected before the discontinuation.
- Among patients who completed, patients with greater decline from baseline in the functional measurement are ranked worse.
- If it is not possible to assign either patient as having the better outcome, then the score assigned to the pair is 0.

For each patient, the assigned scores from the pairwise comparisons with all others will first be summed, and all patients in the analysis population will be ranked according to their summated scores to create a rank score from 1 for the lowest summated score to N (total number of patients in the analysis population) for the highest summated score. If ties occur, each of the tied summated scores will be assigned the average of the ranks the tied summated scores would have if there were no ties.

The rank scores will be analyzed using the generalized Gehan-Wilcoxon test. In addition, the rank scores will be analyzed using an ANCOVA model that adjusts for baseline variables (baseline functional measurement, time from symptom onset, site of disease onset and riluzole or edaravone use). The rank scores between the reldesemtiv and placebo groups will be compared, and the least square mean difference as well as the p-value will be presented.

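### For a year-only ALS onset or diagnosis date, SAP 5.6.3 gives months in multiples of 12, so same-year onset has no defined progression rate and some patients fall in the wrong duration subgroup

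*SAP*

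**What the plan says.** SAP 5.6.3 rules out imputing partial ALS dates. Instead, "The available year or year and month in a partial date will be used to calculate the time from ALS symptom onset and the time" (the sentence goes on to diagnosis, and both times are in months). Three rules apply in order:

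- Full dates: "If the duration in days can be derived based on the available date information, the duration in months will be calculated as" days / 30.4375.
- Year and month only: the derived number of months is used.
- Year only: "If the duration in years can be derived but not the duration in days and months, the duration in months will be calculated as" years × 12.

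The section does not define duration in years. It has no minimum, midpoint or set-to-missing rule for a result of zero.

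SAP 5.5.7 defines the pre-study progression rate: "the rate of disease progression per month evaluated at baseline can be calculated as follows", namely 48 minus the baseline ALSFRS-R total, divided by "months (30.25 days) since ALS symptom onset". It has no rule for a zero denominator and does not refer to 5.6.3.

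These quantities are used in three places:

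- SAP 7.3, subgroups for the primary and both secondary endpoints: "Time since ALS symptom onset (< 2 years, ≥ 2 years"), "Time since ALS diagnosis (< 1 year, ≥ 1 year"), a second diagnosis cut at 6 months, and tertiles of the progression rate.
- SAP 7.9.1, one ANCOVA of the joint-rank scores, adjusted among other variables for "time from symptom onset, site of disease onset and riluzole or edaravone use".
- SAP 6.6, descriptive statistics of time since onset and time since diagnosis.

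**The concern.** With only a year recorded and no imputation, the one duration that can be derived is the difference between two calendar years. Multiplied by 12, it can only be 0, 12, 24, 36 and so on, whatever the month of enrolment. This has two consequences.

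First, onset in the baseline year gives 0 months, and the rate becomes a division by zero.

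Second, 12 and 24 months fall exactly on the 1-year and 2-year cut-offs. The boundary value belongs to the longer-duration group, so every such patient goes there even when the true duration is well short of the cut.

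At stake are the classification behind four subgroup factors, the accuracy of the baseline disease-history table, and one exploratory covariate. In addition, 5.5.7 uses a 30.25-day month where 5.6.3 uses 30.4375 for the same quantity.

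**Working it through.** The documents state no figure on this point, so there is none to reproduce. The check applies the rule and compares it with the true duration.

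**Set-up.** Let D be the calendar-year difference, f the fraction of the year elapsed at baseline, and u the fraction elapsed at the event (onset or diagnosis).

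- True months = 12(D + f − u).
- Rule = 12D.
- Error (rule minus truth) = 12(u − f).

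Assumption, not from the documents: u and f are independent and uniform on (0, 1), with the event before baseline when D = 0. An enumeration of every 2018 baseline day against every event day, at 30.4375 days per month, agreed with the formulas below.

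**Size of error.** For D ≥ 1:

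- Mean error at a given f is 12(0.5 − f): about +6 months for January baselines, −6 for December, and 0 over the year.
- RMS error of the rule is 12 × √(1/6) = 4.90 months.
- RMS error with a mid-year date is 12 × √(1/12) = 3.46 months.

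**Misclassification at the SAP 7.3 cuts.**

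| Cut | D | Rule (months) | True range (months) | Misplaced by rule | Misplaced by mid-year date |
|---|---|---|---|---|---|
| Onset, 2 years | 2 | 24 | 12.0 to 36.0 | 50% | 25% |
| Diagnosis, 1 year | 1 | 12 | 0.03 to 23.95 | 50% | 25% |
| Diagnosis, 6 months | 0 | 0 | 0.03 to 11.96 | 25% | 25% |
| Diagnosis, 6 months | 1 | 12 | 0.03 to 23.95 | 12.5% | 12.5% |

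- D = 1 at the 1-year cut: the truth is under 12 months when u > f, which has probability 0.5.
- A mid-year date errs there only when f ≥ 0.5 and u > f, or f < 0.5 and u < f: 0.125 + 0.125 = 0.25.
- D = 1 at 6 months: u − f > 0.5, probability 0.125.
- D = 0 at 6 months: 0.125 / 0.5 = 0.25. The comparator for D = 0 is the midpoint between 1 January and baseline.
- Nobody is misplaced at the onset cut for D = 0, 1 or 3, or at the 1-year diagnosis cut for D = 0 or 2.

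**Examples**, with an assumed ALSFRS-R total of 38 where a rate is needed:

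- Onset 10 Jan 2018 recorded as 2018, baseline 15 Nov 2018: 309 days. Truth is 309/30.4375 = 10.2 months and the 5.5.7 rate is 10/(309/30.25) = 0.98 per month. The rule gives 10/0.
- Onset 10 Dec 2016 recorded as 2016, baseline 15 Jan 2018: 401 days, 13.2 months. The rule gives 24, and the rate falls from 0.75 to 10/24 = 0.42 per month.
- Diagnosis 15 Nov 2017 recorded as 2017, baseline 15 Jan 2018: 61 days, 2.0 months. The rule gives 12, which is wrong at both diagnosis cuts.

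**Month length.** 30.25 × 12 = 363 days, and 30.25/30.4375 = 0.994, a difference of 0.6%.

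**Possible numbers.** The sub-totals in SAP Appendix C (pooled site 8 summed from its sites) come to 20 + 53 + 49 + 52 + 61 + 71 + 51 + 36 + 65 = 458. If 2% to 10% had a year-only date (an assumption), that is about 9 to 46 patients. Even if all were diagnosed exactly one calendar year back, about 5 to 23 would be misplaced at the 1-year cut. A mid-year date would correct about half of those, 2 to 11.

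**The case against.** The strongest reply is that nothing confirmatory depends on these durations. That stands. The primary model (SAP 7.5.1), its sensitivity analysis (7.5.2), the secondary models (7.6) and the testing order (7.4) use neither duration nor rate. Onset and diagnosis precede randomisation, so a date error cannot depend on arm. Comparisons within a misassigned subgroup remain randomised, so the error blurs the subgroups and does not favour a treatment.

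It also stands that the calendar-year reading is an inference, and that 5.5.7 does not cite 5.6.3. One could read 5.5.7 as needing a duration in days, so that a year-only onset simply has a missing rate. That does not close the gap: the SAP would then have no stated rule for these patients, and their place in the tertile analysis would still be unspecified.

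Year-only diagnosis dates may be rare, since protocol inclusion criterion 3 requires diagnosis within 24 months of screening, and a same-year onset with no month should be rarer still. Not imputing is a deliberate policy, also applied to medications in 5.6.2. On the other hand, 5.6.4 already uses fixed conventions for partial adverse-event dates, so a convention here would not be foreign to the plan.

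A reader might infer more than the documents support:

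- That 9 to 46 patients are misclassified. That is an assumed count of year-only dates. No rate is given, and only some year differences are affected.
- That all the 7.3 cuts coincide with values the rule produces. The 6-month cut does not.
- That fast progressors are selectively dropped. The documents hold no data to show it.
- That the two month lengths alter the tertiles. Applied to everyone, 30.25 is a common scale factor and changes no ranking.

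**Conclusion.** The point holds as a minor specification defect. On its only workable reading, the year-only rule leaves the progression rate undefined for same-year onset. It also sends every one-year diagnosis difference and every two-year onset difference to the longer-duration group, misplacing about 50% of such patients where a mid-year date would misplace about 25%. The 6-month diagnosis cut is affected too (25% for same-year, 12.5% for one year back), and a mid-year date does not improve it.

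The percentages rest on dates uniform within the year, and the number of patients concerned is unknown. The consequences are confined to description, subgroups and one exploratory covariate. The point is no reason to doubt the primary or secondary results.

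**What to change.** For these derived durations only, replace a partial date with the midpoint of its feasible interval:

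- Start from the known year, or the known month. The month case matters too, because the month-level rule could give 0 for onset in the baseline month.
- For onset, truncate above at the known diagnosis date (or at screening, if the diagnosis date is itself partial).
- For diagnosis, truncate above at the screening date and below at the 24-month eligibility limit.

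The midpoint is preferable to a fixed 1 July capped at those limits. For a same-year onset with early-year dosing, the cap could move the date to screening, which is at most 14 days before Day 1. That is 14/30.4375 = 0.46 months, and with an ALSFRS-R total of 38 a rate of 10/0.46, about 22 points per month. The midpoint keeps the duration positive without pushing the date to the boundary.

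Then compute months as days / 30.4375 in both 5.6.3 and 5.5.7, have 5.5.7 refer to 5.6.3, and flag imputed dates in the listing of onset and diagnosis dates.

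The cost is a few lines of SAP text and programming before database lock, with no new data. The downside is that a few approximate dates are imputed, and accuracy at the 6-month cut improves only where the truncation narrows the interval.

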5.6.4. Missing Onset and Stop Dates for Adverse Events

For AEs with incomplete date information recorded in the eCRF, the imputation will follow the following algorithm:

1. For missing AE onset Day and Time:
 - If an AE onset Day is missing and the Month of AE onset is known, then the first day of the month of AE onset will be imputed as the AE onset date.
 - If AE onset information is not available, then the first dosing date will be imputed as the AE onset date.
2. For missing AE end Day and Time:
 - If the AE end Day is missing and the AE end Month is earlier or later than that of the Follow-Up Visit, then the last day of the AE end month will be imputed as the AE end date.
 - If the AE end Day is missing and the AE end Month is the same as that of the Follow-Up Visit, then the date of the Follow-Up Visit will be imputed as the AE end date.
 - If no AE end information is available, then
 - For patients who discontinued early from study drug, the imputed AE end date will be on the later of the last dosing date + 28 days or the last visit or contact date.
 - For patients who completed the study, the imputed AE end date and time will be the date of the Follow-Up Visit.
 - If the stop date is missing and the event is ongoing, the event will be noted as ongoing” in the stop date column in data listings.

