7.3. Recording and Reporting of AEs/SAEs

7.3.1. Recording and Reporting of AEs

Events occurring between the Screening Visit and just prior to the first dose of the investigational product on Day 1 should be recorded in the Medical History eCRF unless the event is related to a protocol-mandated procedure. If the event is deemed related to a protocol-mandated procedure (e.g., hematoma at the puncture site) and deemed clinically significant by the Investigator, the event should be reported as an AE or an SAE (if applicable).

AEs will be documented from the first administration of the investigational product through the Follow-Up Visit. The Investigator will review all documentation (e.g., hospital progress notes, laboratory and diagnostic reports) relevant to the event. A diagnosis will then be determined based on signs, symptoms, and/or other clinical information. The diagnosis and not the individual signs/symptoms should be reported as the AE term.

ALS progression and signs/symptoms that are expected as part of ALS progression (see Section 7.4.3) will not be collected as AEs unless they meet seriousness criteria and should be recorded as SAEs.

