5.5.10.2. Adverse Event

AE Duration

The duration (in days) of an adverse event (AE) is calculated as AE stop date - AE start date + 1. If the event is ongoing, the final database lock date will be used as the stop date in duration calculations.

AE Severity

The severity of an AE is based on the Common Terminology Criteria for Adverse Events (CTCAE) grades collected on the CRF:

Grade 1 = Mild

Grade 2 = Moderate

Grade 3 = Severe

Grade 4 = Life threatening

Grade 5 = Fatal

For summary purposes, missing severity will be counted as severe.

AE Relatedness

All AEs classified as treatment related by the investigator on the CRF are considered treatment related. For summary purposes, missing relatedness will be counted as related.

TEAE and Serious TEAE

An AE or serious AE (SAE) will be regarded as treatment emergent if it starts or worsens (eg, increases in severity or frequency) during or after the first dose of study drug.

Death

Date and reason of death will be recorded and presented.

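### An AE with a known onset month but no day is dated to the 1st of that month with no check against first dose, so such events in the first-dose month drop out of the TEAE tables

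*SAP*

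**What the plan says.** SAP 5.6.4 has two rules for incomplete onset dates. With the day missing and the month known, "then the first day of the month of AE onset will be imputed as the AE onset date". With nothing known, "If AE onset information is not available, then the first dosing date will be imputed as the AE onset date". Neither rule compares a known month with the month of first dose.

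SAP 5.5.10.2 makes an event treatment emergent if "it starts or worsens (eg, increases in severity or frequency) during or after the first dose of study drug"; protocol 8.4.5.2 uses the same definition. SAP 8.1.1 builds the main incidence tables from treatment-emergent events only. Their incidence and severity are a secondary endpoint in protocol 2.2.1 and a safety endpoint in SAP 2.2.5.

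On collection, protocol 7.3.1 states that "AEs will be documented from the first administration of the investigational product through the Follow-Up Visit". Events between screening and first dose "should be recorded in the Medical History eCRF unless the event is related to a protocol-mandated procedure".

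**The concern.** A partial onset date in the first-dose month is ambiguous on its face, but protocol 7.3.1 largely resolves it: apart from clinically significant procedure-related events, anything on the AE form began after dosing. The imputation overrides that and places the event before dosing.

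The result is also anomalous within the SAP. An event about which nothing is known counts as treatment emergent; one known to have started in the first-dose month does not.

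The SAP's other defaults go the conservative way:

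- Severity: "For summary purposes, missing severity will be counted as severe".
- Relatedness: "For summary purposes, missing relatedness will be counted as related".
- Partial medication dates are compared with the first-dose date under SAP 5.6.2, and "If the available data do not give sufficient information to classify the medication, the medication will be classified as concomitant medication".

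The AE onset rule has no such comparison and errs the other way. At stake is a one-directional under-count, concentrated on events that start soon after first dose.

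**Working it through.** The plan gives no figure for this rule, so there is none to reproduce. The check applies the rule literally and then asks how often it misdates an event.

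**Example.** First dose is on 15 March and onset is recorded as March, day unknown. The imputed onset is 1 March. By SAP 5.5.3, study day = date of interest − first-dose date = 1 − 15 = −14. The event starts before dosing and is not treatment emergent by onset. Had the month been missing too, onset would be 15 March, study day 1, and the event would count.

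**How many first-dose dates are exposed.** The imputed date precedes first dose unless first dose falls on the 1st. In a 365-day year that is 353 of 365 dates, or 96.7%.

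**Share of post-dose events misdated.** The population is events with the day missing and the month known. Inputs:

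- First-dose dates uniform over the calendar (assumption).
- Onset lag of 0 to L − 1 days after first dose, uniform (assumption). L = 113 corresponds to Day 113, the scheduled Follow-up day in SAP Appendix B.

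An event is misdated when onset falls in the same month and year as first dose and first dose is not on the 1st. In a 30-day month, lag k leaves 29 − k qualifying first-dose days out of 30 (none beyond k = 28). For L up to 29:

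share = [29 − (L − 1)/2] / 30

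For L = 113: share = (29 + 28 + … + 1) / (30 × 113) = 435/3390 = 12.8%.

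Exact enumeration over all 730 dates in 2017–2018 agrees:

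| Onset window | 30-day formula | Enumeration |
|---|---|---|
| Dosing day only (L = 1) | 29/30 = 96.7% | 96.7% |
| First 7 days | 26/30 = 86.7% | 86.8% |
| First 14 days | 22.5/30 = 75.0% | 75.3% |
| First 28 days | 15.5/30 = 51.7% | 52.3% |
| Days 1–113 | 12.8% | 13.0% |

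If onset instead decays exponentially over the 113 days, the enumerated share is 58%, 39% and 30% for mean lags of 14, 28 and 42 days.

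**Share of all adverse events lost.** This is the fraction with the day missing multiplied by the share above. The documents do not give that fraction, so a range is assumed:

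| Day missing (assumed) | All events, uniform onset (× 13%) | Events starting in first 28 days (× 52%) |
|---|---|---|
| 1% | 0.13% | 0.5% |
| 5% | 0.65% | 2.6% |
| 10% | 1.3% | 5.2% |

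**With the correction.** In the example, onset becomes 15 March, study day 1, and the event counts.

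**The case against.** The strongest objection is that the consequence is inferred. SAP 5.6.4 never says that the imputed date sets the treatment-emergent flag, and onset dates also feed the AE duration in SAP 5.5.10.2. A programmer could rely on protocol 7.3.1 and treat every AE-form record as post-dose. This does not rescue the rule. Testing the imputed start against first dose is the natural reading, and neither document states an override, so a programmer who made that correction would be departing from the SAP as written.

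The second objection is size, and much of it stands. The large percentages apply only to events with the day missing and the month known. Visits on Day 1 and at Weeks 2 and 4 keep recall short, and the edit checks and manual review in SAP 5.2 may recover some missing days, so early events could be the least likely to lack one. SAE reports must carry an onset date (protocol 7.3.2). The summaries of SAEs and of AEs leading to discontinuation or death in SAP 8.1.2 are not worded as treatment-emergent only. All events stay in the listings, and a patient counts once per preferred term, so a lost event matters only if it is that patient's only one for the term. These points limit how often the error shows; they do not make the rule right.

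Third, the rule is the same in every arm, and no dose comparison has been shown to change. That is fair: the loss would differ between arms only if onset timing or date completeness did. The primary analysis and the alpha-controlled tests are not affected.

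**Conclusion.** The concern holds. As written, SAP 5.6.4 dates almost any day-missing event in the first-dose month before dosing, and the treatment-emergent definition then excludes it unless worsening after first dose is recorded. The error can only reduce counts in a listed secondary endpoint.

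Among post-dose events with only the day missing, the loss runs from 13% (onset uniform to Day 113) to 52% (onset within 28 days) and higher for earlier onset. As a share of all events it is probably small: 0.13% to 1.3% under uniform onset if 1% to 10% lack a day. These figures rest on evenly spread first-dose dates, the stated onset patterns and an assumed frequency of missing days. The defect in the rule depends on none of them. It should be corrected, although it does not threaten the trial's main conclusions.

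**What to change.** Add to SAP 5.6.4: if the onset day is missing and the known onset month and year equal those of first dose, impute the first-dose date, unless the AE end date is before first dose or other recorded information shows that the event began earlier; otherwise impute the first day of the month as now. It would help to state at the same time that ambiguous cases count as treatment emergent, that the imputed date is the one used for the flag, and what is done when only the year is known, which 5.6.4 does not cover.

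The cost is a sentence or two in the SAP and a small change to the AE dataset program. SAP 5.3 treats a difference in data handling as requiring a SAP revision, and SAP 1 puts analysis decisions before database lock, so the change should be made by then. Treatment-emergent counts may become slightly less favourable. A rare procedure-related pre-dose event with a missing day could be counted as treatment emergent when nothing on record shows its earlier onset; that errs in the same conservative direction as the SAP's other defaults.
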